15.1 Serious Adverse Event (SAE) Reporting

- An adverse event is considered serious if it results in ANY of the following outcomes: Death
- A life-threatening adverse event
- An adverse event that results in inpatient hospitalization or prolongation of existing hospitalization
- A persistent or significant incapacity or substantial disruption of the ability to conduct normal life functions
- A congenital anomaly/birth defect
- Important Medical Events (IME) that may not result in death, be life threatening, or require
 hospitalization may be considered serious when, based upon medical judgment, they may
 jeopardize the patient or participant and may require medical or surgical intervention to prevent
 one of the outcomes listed in this definition
- An overdose

Note: Hospital admission for a planned procedure/disease treatment is not considered an SAE.

Refer to Table 3 for additional details regarding each of the above criteria.

SAE reporting is required as soon as the participant starts investigational treatment/intervention. SAE reporting is required for 30-days after the participant's last investigational treatment/intervention. Any event that occur after the 30-day period that is unexpected and at least possibly related to protocol treatment must be reported.

Please note: Any SAE that occurs prior to the start of investigational treatment/intervention and is related to a screening test or procedure (i.e., a screening biopsy) must be reported.

All SAEs must be submitted in PIMS. If an SAE requires submission to the HRPP office per IRB SOP RR-408 'Reporting of Serious Adverse Events', the SAE report must be submitted within 5 calendar days of the event. All other SAEs must be submitted within 30 calendar days of the event.

The report should contain the following information:

- The date the adverse event occurred
- The adverse event
- The grade of the event
- Relationship of the adverse event to the treatment(s)
- If the AE was expected

- Detailed text that includes the following
- An explanation of how the AE was handled
- A description of the participant's condition
- Indication if the participant remains on the study
- If an amendment will need to be made to the protocol and/or consent form
- If the SAE is an Unanticipated Problem

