• Cohort C: Patients without any of the above HR-gene alterations included in Cohort A and B who have platinum-sensitivity, which is defined as durable response of either a partial response (PR) or complete response (CR) during at least 6 months on platinum-based therapy. Variants of unknown significance of candidate HR-genes from Cohort A or B will be eligible for Cohort C if they meet the partial response to platinum criterion.

All the participating patients will receive the combination of pembrolizumab 200 mg IV every 3 week and olaparib 300 mg twice day orally daily continuously (POLAR) as a maintenance therapy. After the first 6 months (9 cycles), on C10D1 Pembrolizumab 400 mg IV every 6 week plus olaparib 300 mg twice a day orally will be continued. Per treating investigator's discretion, patients may remain at Pembrolizumab 200 mg IV every 3 weeks after the first 9 cycles. Additionally, to accomodate patients traveling far distances, if, per treating investigator, after the first or second imaging, there are no toxicities, patient's dosing of Pembrolizumab may change to 400 mg IV every 6 weeks. All cycles will be 21-days (3 weeks) in length.

Figure 1. Schema for Genetic and Response Eligibility Criteria:

Number of trial participants	63 (Cohort A: 33, Cohort B: 15, Cohort C: 15)
Estimated enrolment period	3 years
Estimated duration of trial	7.5 years
Duration of Participation	4 years

Estimated average length of	4 months
treatment per participant	

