10.2 Timing of Dose Administration

Trial treatment should be administered on Day 1 of each cycle after all procedures or assessments have been completed as detailed on the Trial Flow Chart (Section 6.0). Trial treatment may be administered up to 3 days before or after the scheduled Day 1 of each cycle due to administrative reasons. On the day of the treatment, participants can receive oral olaparib AM dose at the clinic visit followed by pembrolizumab.

All trial treatments will be administered on an outpatient basis.

Pembrolizumab will be infused per MSK guidelines. Pembrolizumab 200 mg will be administered as a 30-minute IV infusion every 3 week. After the first 6 months (9 cycles), on C10D1 Pembrolizumab 400 mg IV every 6 week plus olaparib 300 mg twice a day orally will be continued. Pembrolizumab 200 mg IV every 3 weeks may continue after Cycle 9, and Pembrolizumab 400 mg IV every 6 weeks may begin earlier than Cycle 9 per treating physician's discretion. Given the variability of infusion pumps a window of -5 minutes and +10 minutes is permitted (i.e., infusion time is 30 minutes: -5 min/+10 min).

8

POLAR: a phase 2 trial for pembrolizumab and olaparib maintenance for metastatic PDAC and HRD and/or Exceptional Response to Platinum – Ver. 5/3/2020

10.3 Dose Modification and Toxicity Management for Immune-Related AEs Associated with Pembrolizumab

AEs associated with pembrolizumab exposure may represent an immunologic etiology. These immune-related AEs (irAEs) may occur shortly after the first dose or several months after the last dose of pembrolizumab treatment and may affect more than on body system simultaneously. Therefore, early recognition and initiation of treatment is critical to reduce complications. Based on existing clinical study data, most irAEs were reversible and could be managed with interruptions of pembrolizumab, administration of corticosteroids and/or other supportive care. For suspected irAEs, ensure adequate evaluation to confirm etiology or exclude other causes. Additional procedures or tests such as bronchoscopy, endoscopy, skin biopsy may be included as part of the evaluation. Based on the severity of irAEs, withhold or permanently discontinue pembrolizumab and administer corticosteroids. Dose modification and toxicity management guidelines for irAEs associated with pembrolizumab are provided in Table 3.

Table 3 Dose modification and toxicity management guidelines for immune-related AEs associated with pembrolizumab

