10.6.1.1 Management of prolonged hematological toxicities while on POLAR treatment

If a patient develops prolonged hematological toxicity such as:

- ≥2 week interruption/delay in study treatment due to CTC grade 3 or worse anemia and/or development of blood transfusion dependence
- ≥2 week interruption/delay in study treatment due to CTC grade 3 or worse neutropenia (ANC < 1 x 10⁹/L)
- ≥2 week interruption/delay in study treatment due to CTC grade 3 or worse thrombocytopenia and/or development of platelet transfusion dependence (Platelets < 50 x 10⁹/L)

Check weekly differential blood counts including reticulocytes and peripheral blood smear. If any blood parameters remain clinically abnormal after 4 weeks of dose interruption, the patient should be referred to hematologist for further investigations. Bone marrow analysis and/or blood cytogenetic analysis should be considered at this stage according to standard hematological practice. Study treatment should be discontinued if blood counts do not recover to CTC G 1 or better within 4 weeks of dose interruption.

Development of a confirmed myelodysplastic syndrome or other clonal blood disorder should be reported as an SAE and full reports must be provided by the investigator to Merck Patient Safety. Olaparib treatment should be discontinued if patient's diagnosis of MDS and/or AML is confirmed.

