11.0 EVALUATION DURING TREATMENT/INTERVENTION

11.1 Adverse Event (AE) Monitoring

The investigator or qualified designee will assess each participant to evaluate for potential new or worsening AEs as specified in the Trial Flow Chart and more frequently if clinically indicated. Adverse experiences will be graded and recorded throughout the study and during the follow-up period according to NCI CTCAE Version 5.0 (see Appendix 2). Toxicities will be characterized in terms regarding seriousness, causality, toxicity grading, and action taken with regard to trial treatment.

Memorial Sloan Kettering Cancer Center IRB Number: 20-481 A(11)

Approval date: 11-Jun-2024 Page | **39**

All assessments will be performed on the day of the scheduled visit date unless a time window is specified. Assessments scheduled on the days of study treatment should be performed before the infusion of study drug(s) unless otherwise noted. If the timing of a study visit coincides with a holiday, weekend, or other administrative disruption that precludes the visit, the visit should be scheduled on the nearest following feasible date, with subsequent visits rescheduled accordingly.

Table 9. Schema for treatment and evaluations.

Trial Period:	Screening Phase		Trea	ıtmen	ıt Cy	cles	(21 D	ay C	ycles)	Pembro Q6 Wk		End of Treatment	Post-Treatment	
Treatment Cycle/Title:	Pre- screening (Visit 1)	1	2	3	4	5	6	7	8	9	Even Cycles (ex. 10, 12, 14 etc.)	Odd Cycles (ex. 11, 13, 15, etc.)	Discontinua tion	Safety Follow-up (in clinic)	Survival Follow- Up (Clinic or phone)
Scheduling Window (Days):	-28		± 3	± 3	± 3	At time of Discontinua tion	30 days and 60 days post discontinuation	Every 12 weeks for 5 years							
Administrative Procedures															
Informed Consent	Х														
Inclusion/Exclusion Criteria	Х														
Demographics and Medical History	Х														
Prior and Concomitant Medication Review	х	х	х	Х	х	х	х	х	х	Х	Х	X**	х	Х	Х
Pembrolizumab** Administration		х	х	Х	Х	х	х	х	х	х	Х	X**			
Survival Status	Х	Х	Х	Х	Х	Х	Х	Х	Х	Х	Х	X**	Х	Х	Х
Clinical Procedures/A	Clinical Procedures/Assessments														
Review Adverse Events		х	Х	X	Х	Х	Х	Х	Х	Х	X	X**	Х	Х	×
Full Physical Examination	Х	х	Х	х	Х	Х	х	х	х	х	х		Х		

Trial Period:	Screening Phase		Trea	ıtmer	nt Cy	cles	(21 C	ay C	ycles)	Pembro Q6 Wk End of Treatment			Post-Treatment	

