12.0 CRITERIA FOR REMOVAL FROM STUDY

- **12.1. Disease Progression:** Patients with confirmed progressive disease following POLAR treatment will be removed from treatment, their disease pathologically documented, and the patient will be followed for survival and the immunologic endpoints. However, in the absence of unacceptable toxicity, participants who meet criteria for disease progression per RECIST 1.1 while receiving treatment will be permitted to continue treatment if in the opinion of the treating MD the patient is continuing to derive benefit from the treatment. iRECIST will be used to evaluate the response and the co-primary endpoint of overall response rate will be assessed both by RECIST and iRECIST.
- **12.2 Extraordinary Medical Circumstances:** If at any time the constraints of this protocol are detrimental to the patient's health, the patient shall be withdrawn from treatment. In this event:
 - 12.2.1. Document reasons for withdrawal and record whether this action was patient or physician directed.
 - 12.2.2. The patient will remain technically on-study although treatment has been discontinued. The patients will be followed for relapse and survival.

12.3. Unexpected or Life-Threatening Toxicity (CTCAE v5.0 Table):

- 12.3.1. Direct questions regarding drug therapy to the Principal Investigator.
- 12.3.2. Reporting requirements and procedures depend upon:
 - (1) whether agents are suspected of causing toxicity, (2) whether possibility of such toxicity was reported in the consent form, or manufacturer's literature (Published Toxicity), (3) the severity or grade of the toxicity.
- 12.3.3. Expected toxicities:
- 12.3.3.1. Grade 4 myelosuppression: Report only as part of regular data submission.
- 12.3.3.2. All other toxicities, Grades 4: Written Report to Principal and Co-Investigators, within 10 working days.
- 12.3.3.3. All other toxicities, Grades 1 to 3: Report only as part of regular data submission.
- 12.3.4. Unexpected Toxicities: Unexpected toxicities are toxicities that are not listed in the toxicity management section of the protocol, the consent form, or the manufacturer's package inserts. All unexpected toxicities will be reported to Principal and Co-Investigators, within 10 working days.
- 12.4. Patient noncompliance with the protocol requirements
- 12.5. Patient request to withdraw
- 12.6. Development of serious intercurrent illness during treatment
- 12.7. Patient removed at the discretion of the PI

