If a patient requires discontinuation of either olaparib or pembrolizumab for reasons of toxicity and if in the opinion of the treating MD the patient is continuing to derive benefit, the patient is able to continue on study.

- All AEs from the time of treatment allocation/randomization through 30 days following cessation of study treatment must be reported by the investigator.
- All AEs meeting serious criteria, from the time of treatment allocation/randomization through 90
 days following cessation of study treatment, or 30 days following cessation of study treatment if the
 participant initiates new anticancer therapy, whichever is earlier must be reported by the investigator.
- All pregnancies and exposure during breastfeeding, from the time of treatment allocation/randomization through 120 days following cessation of study treatment, or 30 days

following cessation of study treatment if the participant initiates new anticancer therapy must be reported by the investigator.

 Additionally, any SAE brought to the attention of an investigator at any time outside of the time period specified above must be reported immediately by the investigator if the event is considered to be drug-related.

Investigators are not obligated to actively seek AE or SAE or other reportable safety events in former study participants. However, if the investigator learns of any SAE, including a death, at any time after a participant has been discharged from the study, and he/she considers the event to be reasonably related to the study treatment or study participation, the investigator must promptly notify Merck.

Possible Side Effects of pembrolizumab

COMMON, SOME MAY BE SERIOUS

In 100 people receiving pembrolizumab more than 20 and up to 100 may have:

- Itching of the skin
- Loose or watery stools
- Cough

OCCASIONAL, SOME MAY BE SERIOUS

In 100 people receiving pembrolizumab from 4 to 20 may have:

- Joint pain
- Rash
- Fever
- Back pain
- Pain in the belly
- Loss of skin color
- Not enough thyroid hormone (hypothyroidism), which may make you feel tired, gain weight, feel cold, or have infrequent or hard stools
- Low levels of salt in the blood (hyponatremia), which may make you feel tired, feel confused, have a headache, have muscle cramps, and/or feel sick to your stomach
- Inflammation of the lungs (pneumonitis), which may make you feel short of breath and cough

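### Sections 15.0 and 15.1 set conflicting rules for reporting late serious adverse events; separately, the 5-year follow-up does not fit the stated participation and trial lengths

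*Protocol*

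**What the plan says.** **Late events.** Section 15.1 requires SAE reports from the start of treatment until 30 days after the last treatment. For anything later it says: "Any event that occur after the 30-day period that is unexpected and at least possibly related to protocol treatment must be reported". The same section sends SAEs to the institutional system and sets deadlines of 5 or 30 calendar days.

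Section 12.3.4 holds the only definition of unexpected that I find in the protocol: "Unexpected toxicities are toxicities that are not listed in the toxicity management section of the protocol", nor in the consent form or the package inserts.

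The toxicity management sections do list delayed toxicities. Section 10.3 says that immune-related events "may occur shortly after the first dose or several months after the last dose of pembrolizumab treatment". Section 10.6.1.1 on prolonged hematological toxicity says: "Development of a confirmed myelodysplastic syndrome or other clonal blood disorder should be reported as an SAE". Its next sentence deals with confirmed MDS and AML.

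Section 15.0 is different. Its SAE window runs to 90 days after treatment stops, or to 30 days if new anticancer therapy begins. Outside the window, any drug-related SAE brought to the investigator's attention must be reported at once, with no condition on expectedness. It adds: "Investigators are not obligated to actively seek AE or SAE or other reportable safety events in former study participants". The sentence after that requires prompt notice to the drug supplier if the investigator nevertheless learns of a related SAE.

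Table 9 schedules in-clinic safety visits at 30 and 60 days after discontinuation and then survival contacts "Every 12 weeks for 5 years". Adverse event review is marked for both.

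**Durations.** The summary table in Section 1.0 gives 3 years of enrolment, a 7.5-year trial, an average of 4 months on treatment and, in the row "Duration of Participation", 4 years. Section 7.0 expects accrual in about 2.5 to 3 years.

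**The concern.** A site needs one answer to a simple question: is a serious, related, already known toxicity reportable if it appears after day 30? Section 15.0 says yes. Section 15.1, whose title and deadlines make it the section staff will consult for SAE reporting, asks only for unexpected events.

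The events caught between the two rules are those that the protocol itself expects to be delayed. Olaparib carries an MDS/AML provision, and pembrolizumab carries a statement that immune-related events can appear months after the last dose. Section 16.4 ends the monitoring committee's review once accrual is closed and no participant is on active therapy. Late events then depend on the SAE rules, which disagree.

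The duration figures raise a smaller question: can the follow-up in which late toxicity and OS would be observed be completed within the stated lengths?

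**Working it through.** **Late events.** Take a serious event, judged related, of a type named in the toxicity management sections, and apply each rule. The last column assumes that the 12.3.4 definition governs 15.1.

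| When found | Section 15.0 | Section 15.1 |
|---|---|---|
| By day 30 | Required | Required |
| 60-day safety visit, no new anticancer therapy | Required (inside the 90-day window) | Not required (after day 30, expected) |
| 60-day safety visit, new anticancer therapy begun | Required (window closed, but drug-related at any time) | Not required |
| Later survival contact | Required if drug-related and it comes to attention | Not required |

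A confirmed MDS or other clonal disorder is in addition an SAE under Section 10.6.1.1. That sentence has no time limit, although its subsection heading refers to the time on POLAR treatment.

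The rules agree up to day 30 and differ at every later scheduled visit or contact. The disagreement does not depend on 12.3.4: Section 15.0 has no expectedness condition, so under any definition of unexpected the two differ for events that count as expected. The definition only decides which events those are.

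The recipients do not settle it. Section 15.1 names the institutional system, while 15.0 and 10.6.1.1 name the drug supplier for certain reports. The protocol does not say whether these are separate streams. If they are, the institutional stream has the gap; if they are one, two rules conflict.

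**Durations.** Inputs: enrolment 3 years (Section 1.0) or 2.5 (lower figure, Section 7.0); treatment 4/12 = 0.33 year; follow-up 5 years (Table 9, post-treatment column).

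- The summary table agrees with itself: 3 + 4 = 7.0 years, within 7.5.
- Participation with Table 9: 0.33 + 5 = 5.33 years, against 4.
- Trial length, last participant: 3 + 0.33 + 5 = 8.33 years, against 7.5. With 2.5-year accrual: 2.5 + 0.33 + 5 = 7.83.
- If the 5 years are counted from treatment start: 3 + 5 = 8.0, or 2.5 + 5 = 7.5. Only this last variant meets 7.5, and 5 years still exceeds 4.
- Follow-up available to the last participant at 3-year enrolment: 7.5 − 3 − 0.33 = 4.17 years.
- Follow-up within 4 years of participation: 4 − 0.33 = 3.67 years. At 84-day intervals that is 3.67 × 365.25 / 84 = 15.9 contacts, against 5 × 365.25 / 84 = 21.7 for the full schedule.

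No variant satisfies all the stated lengths.

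**The case against.** The strongest reply is that the events are covered elsewhere. A reader might infer from 15.1 that the protocol exempts late MDS/AML and late immune-related events. The document does not support that: 15.0 requires any drug-related SAE at any time, its window runs to 90 days unless new therapy starts, and 10.6.1.1 makes confirmed MDS an SAE. This part of the reply stands in full. What remains is that 15.1 says something different.

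A reader might also infer that late events could surface only at the 12-weekly survival contacts. That is not so either. Table 9 has safety visits at 30 and 60 days with adverse event review, and marks the review at survival contacts as well. Section 15.0's statement about not actively seeking events concerns former participants, and people in scheduled follow-up are not clearly that.

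It can further be said that 12.3.4 governs reports to the principal and co-investigators, and that nothing extends its definition to 15.1. That is fair, and it is why the consequence for MDS/AML and immune-related events is stated conditionally. Section 15.1 offers no definition of its own, however, and part of its routing rests on an institutional procedure that is not in the document.

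On durations, most of the summary figures are labelled as estimates, though participation is not. OS is a secondary endpoint analysed by Kaplan-Meier, which accommodates censoring. This limits the point to one of consistency.

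**Conclusion.** The contradiction between 15.0 and 15.1 is real and should be corrected. It applies to serious, related, expected events after day 30. If 12.3.4 defines unexpected, that group includes the delayed toxicities the protocol names. Actual under-reporting cannot be inferred: it would take a site that follows 15.1 alone and sets aside 15.0, 10.6.1.1 and the adverse event review in Table 9.

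The duration mismatch is a separate and minor point. Five years of follow-up against 4 years of participation is inconsistent on any reading. The excess over the 7.5-year trial is 0.83 year at 3-year enrolment and 0.33 year at 2.5, assuming the 4-month average treatment and follow-up counted from discontinuation. Longer treatment widens it: the imaging schedule provides for participants on study beyond 2 years, and 2 years of treatment would give 3 + 2 + 5 = 10 years. The 6-month PFS and ORR decision rules are unaffected by either point.

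**What to change.** Replace the late-event sentence in Section 15.1 with: *Any serious adverse event after this period that is at least possibly related to protocol treatment, whether expected or not, must be reported.* Simply removing the expectedness condition would not do. The present sentence speaks of any event, so non-serious related events would become reportable without end, against the 30-day limit for AEs in 15.0. State whether the institutional and drug-supplier reports follow the same rule. The 30-day and 90-day windows belong to the same conflict and should be reconciled in the same amendment, since the new sentence does not settle them.

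For the durations, either restate participation as treatment plus 5 years and the trial duration as about 8.3 years, or shorten the Table 9 follow-up to fit 4 and 7.5 years.

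The cost is amendment wording and a few more SAE reports, plus a longer stated trial duration if the 5 years are kept. No new visits are needed.

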15.2 Evaluating Adverse Events

An investigator who is a qualified physician will evaluate all adverse events according to the NCI Common Terminology for Adverse Events (CTCAE), version 5.0. Any adverse event which changes CTCAE grade over the course of a given episode will have each change of grade recorded on the adverse event case report forms/worksheets.

All adverse events regardless of CTCAE grade must also be evaluated for seriousness.

An investigator who is a qualified physician, will evaluate all adverse events. Table 3. Evaluating Adverse Events

